#### **7.4.2.3 Dose Reductions**

Per protocol, there will be no dose escalations or reductions of nivolumab and ipilimumab. However, for chemotherapy, dose reduction is permitted according to local standard or local package insert. This information will be retrieved from CRF dosing pages.

For subjects treated with chemotherapy, the following will be summarized by treatment group:

- Number of subjects with at least one dose reduction along with the reason for the dose reduction.

#### **7.4.3 Concomitant Medications**

Concomitant medications, defined as medications other than study medications which are taken at any time on-treatment (ie, on or after the first day of study therapy and within 100 days following the last dose of study therapy), will be coded using the WHO Drug Dictionary.

The following summary tables will be provided:

- Concomitant medications (subjects with any concomitant medication, subjects by medication class and generic term).

A by-subject listing will accompany the table.

Prior medications, defined as non-study medications with a start date before consent date, and current medications, defined as non-study medications with a start date before the first date of study medication and stop date after consent date, will be coded using the UMC WHO Drug Global Dictionary.

The following summary table will be provided:

- Prior/current medications (subjects with any prior/current medication, subjects by medication class and generic term)

By-subject listings will accompany the tables.

##### **7.4.3.1 Immune Modulating Medication**

Immune modulating concomitant medications are medications entered on an immune modulating medication form or available from the most current pre-defined list of immune modulating

medications. The list of anatomic class, therapeutic class and generic name used for the selection at the time of the database lock will be provided.

The percentage of subjects who received immune modulating concomitant medication for

- management of adverse event
- premedication
- other use
- any use
- management of drug-related select adverse event (any grade, grade 3-5) by select AE category/subcategory
- management of IMAEs (any grade, grade 3-5) by IMAE category will be reported separately for each treatment group (percentages of treated subjects by medication class and generic term).

For each category/subcategory of drug-related select AEs (any grade, grade 3-5) and IMAEs (any grade, grade 3-5), the following will be reported for each treatment group:

- The total immune modulating medication treatment duration (excluding overlaps), duration of high dose of corticosteroid, initial dose of corticosteroid, and tapering duration (summary statistics)

Duration represents the total duration the subject received the concomitant medication of interest. If the subject took the medication periodically, then DURATION in the summation of all use. Initial dose represents the dose of the concomitant medication of interest received at the start of the event. In the case multiple medications started on the same date, the highest equivalent dose is chosen and converted to mg/kg by dividing by the subject's recent weight.

These analyses, except the ones related to IMAEs will be conducted using the 30-day safety window. The analyses related to IMAEs will be conducted using the 100-day safety window.

#### **7.4.3.2 Subsequent Therapy**

Number and percentage of subjects receiving subsequent therapies will be summarized for randomized subjects with PD-L1 CPS $\geq$ 5 subjects and all randomized subjects. Categories include:

- Immunotherapy including commercial Nivolumab (anti-PD1 agents, anti-PD-L1 agents, anti-CTLA-4 agents and others) by drug name
- Other anti-cancer agents excluding all immunotherapy (approved and investigational) by drug name
- Surgery for treatment of tumors (ie reason of tumor resection palliative or tumor resection curative)
- Radiotherapy for treatment of tumors (ie, radiotherapy with reason curative or palliative)
- Any combination of the above

A subject listing of follow-up therapy will also be produced for subjects who had any subsequent therapy.

## 7.5 Efficacy

Analyses of progression free survival and objective response rate will be based on the Blinded Independent Central Review (BICR) evaluation, unless noted otherwise.

Analyses in this section will be tabulated for all randomized subjects by treatment group as randomized, unless otherwise specified.

Unless stated otherwise, whenever a stratified analysis is specified, the following stratifications factors (recorded at randomization as per IRT) will be used see Table 7.5-1

**Table 7.5-1: Stratification Factors Used for Stratified Analyses**

[figure not shown]
	Nivo+ipi vs. Chemotherapy	Nivo+chemo vs. Chemotherapy
	
 
• Region (Asia vs. US vs. RoW)
 
• ECOG performance status (0 vs. 1)
 
• PD-L1 expression level (<math>\geq 1\%</math> vs. <math>< 1\%</math> or indeterminate)
 
	
 
• Region (Asia vs. US vs. RoW)
 
• ECOG performance status (0 vs. 1)
 
• PD-L1 expression level (<math>\geq 1\%</math> vs. <math>< 1\%</math> or indeterminate)
 
• Chemotherapy (XELOX vs. FOLFOX)
 

### 7.5.1 Strong Control of Type I Error for Primary and Secondary endpoints:

The following testing strategy guarantees a strong control of FWER at level  $\alpha$  of 5% for the primary and key secondary endpoints.

For the 2 primary endpoints of PFS and OS in the comparison of nivo+chemo vs. chemo in randomized CPS  $\geq 5$  subjects, 2% is allocated to PFS and 3% is allocated to OS. For the first secondary endpoint of OS in nivo+ipi vs. chemo in randomized CPS  $\geq 5$  subjects, alpha will be passed from both PFS and OS as shown in [Figure 7.5.1-1](#), the other secondary endpoints formally tested are also illustrated in the figure.

**Figure 7.5.1-1: Graphical Approach for Primary and Secondary Endpoints**

In the graph, each vertex corresponds to a hypothesis to be tested. The square represent the hypotheses for the primary endpoints and the circles for secondary endpoints, light blue color represent comparison for nivo+ipi vs. chemo and dark blue represent comparison of nivo+chemo vs. chemo. The numbers next to the vertices are the initially allocated (endpoint-specific) significance levels. It is 0 for all secondary endpoints meaning that they cannot be tested until alpha is passed to them from the primary endpoints. The weight (in rectangular frame) associated with a directed edge (line) between any two vertices indicates the fraction of the (local)

significance level at the initial vertex that is added to the significance level at the terminal vertex, if the hypothesis at the tail is rejected.

Table 7.5.1-1 shows the significance levels for the primary and key secondary endpoints. For endpoints which have an interim analysis, the significance level will be distributed using the Lan-DeMets alpha spending function with O'Brien-Fleming boundaries. The nominal significance levels for OS in randomized PD-L1 CPS  $\geq 5$  subjects in Table 7.5.1-1 are those obtained with the number of events exactly as in the table and assuming a prevalence rate of 35% for PD-L1 CPS  $\geq 5$ . At time of analysis, the significance levels will be adjusted according to actual number of events and using the estimated final number of events. For interim analyses of OS in randomized PD-L1 CPS  $\geq 1$  subjects and all randomized subjects, the nominal significance levels will be obtained using the same information fraction as for randomized PD-L1 CPS  $\geq 5$  subjects. At the final analysis the significance level will be calculated using the number of events in the database at time of database lock and considering the  $\alpha$ -level already spent at interim analysis as well as the actual correlation among the test statistics.

**Table 7.5.1-1: Significance Levels for Primary and Secondary Endpoints**

Analysis Timepoint	PFS Nivo+chemo in CPS $\geq 5$		OS Nivo+chemo in CPS $\geq 5$		OS Nivo+ipi in CPS $\geq 5$	
	Event	Sign. level	Event	Sign. level	Event	Sign. level
12 months follow-up	497 a	0.02	395 b	0.0164	NA	NA
24 months follow-up	NA	NA	466 b	0.0252	240 c	0.015 d 0.02 0.035

a Estimated based on 2-piece hazard ratio with HR of 1 for the first 3 months followed by constant HR of 0.56 and assuming 35% prevalence for PD-L1 CPS  $\geq 5$ .

b Estimated based on 2-piece hazard ratio with HR of 1 for the first 6 months followed by constant HR of 0.65 and assuming 35% prevalence for PD-L1 CPS  $\geq 5$ .

c Estimated based on hazard ratios as in Table 5.2.1-3

d The significance level will depend on whether only one primary endpoint was positive or both. If only OS of nivo+chemo in CPS  $\geq 5$  is positive then the significance level is 0.015, if only PFS of nivo+chemo in CPS  $\geq 5$  is positive then the significance level is 0.02 and if both are positive then the significance level is 0.035. The other secondary endpoints for nivo+ipi vs. chemo (OS in all randomized and TTSD) will be tested hierarchically at the same significance level as OS nivo+ipi in CPS  $\geq 5$  subjects.

At the first analysis timepoint, PFS final analysis and OS interim analysis for nivo+chemo vs. chemo in CPS  $\geq 5$  subjects will be tested.

- If none of the primary endpoints can be rejected then no secondary endpoints are tested, and the study continues to proceed to the final OS analysis.
- If PFS is rejected, its entire alpha is passed to OS of nivo+ipi vs. chemo in PD-L1 CPS  $\geq 5$  subjects.
- If OS is rejected at interim analysis, then its alpha (0.03) will be shared equally to OS of nivo+ipi vs. chemo in PD-L1 CPS  $\geq 5$  subjects and to OS of nivo+chemo vs. chemo in PD-L1 CPS  $\geq 1$  subjects.

At the second analysis timepoint, OS final analysis for nivo+chemo vs. chemo in CPS  $\geq 5$  subjects will be tested.

- If this endpoint cannot be rejected then none of the other secondary endpoints for nivo+chemo will be tested. OS for nivo+ipi vs. chemo in CPS  $\geq 5$  subjects can be tested only if PFS for nivo+chemo in CPS  $\geq 5$  subjects was positive, the testing will be done at the significance level of 0.02.
- If OS of nivo+chemo vs. chemo in PD-L1 CPS  $\geq 5$  subjects is statistically significant then its alpha (0.03) will be shared equally to OS of nivo+ipi vs. chemo in PD-L1 CPS  $\geq 5$  subjects and to OS of nivo+chemo vs. chemo in PD-L1 CPS  $\geq 1$  subjects. The testing of OS for nivo+ipi vs chemo will be conducted with significance level of 0.015 or 0.035 (if PFS for nivo+chemo in CPS  $\geq 5$  subjects was positive).

## **7.5.2 Nivo + Chemo vs. Chemo Comparison**

### **7.5.2.1 Analysis of Progression-Free Survival**

PFS (primary definition) as assessed by BICR in randomized CPS  $\geq 5$  subjects will be compared between nivo+chemo vs. chemo, using a two-sided log rank test, stratified by the stratification factors as specified in [Table 7.5-1](#). A significance level of 0.02 will be used. The estimate of the PFS hazard ratio between treatment groups will be calculated using a stratified Cox proportional hazards model, with treatment as the sole indicator covariate (for nivo+chemo vs. chemo arms). Ties will be handled using the exact method. A two-sided 98% CI for the hazard ratio will also be presented.

The PFS function for each treatment group will be estimated using the KM product limit method and will be displayed graphically. A two-sided 95% CI for median PFS in each treatment group will be computed via the log-log transformation method. PFS rates at fixed time points (eg, 6, 12, 18 months, depending on the minimum follow-up) will be presented along with their associated 95% CIs. These estimates will be derived from the Kaplan Meier estimate and corresponding CIs will be derived based on Greenwood formula for variance derivation and on log-log transformation applied on the survivor function.

The source of PFS event (progression or death) will be summarized by treatment group. The status of subjects who are censored (as per primary definition of PFS) in the PFS KM analysis will be tabulated for each treatment group including the following categories:

- On-study (on-treatment, in follow-up)
- Off-study (lost to follow-up, withdraw consent, never treated)
- No baseline tumor assessment
- No on-study tumor assessment and no death
- Received subsequent anticancer therapy

A by-subject listing of lesion evaluations per BICR will be presented.

### **7.5.2.2 Supportive Analyses of Progression-Free Survival**

Sensitivity analyses to examine assumptions of the stratified Log-rank test and Cox model:

- 1) To examine the assumption of proportional hazards in the Cox regression model, in addition to treatment, a time-dependent variable defined by treatment by time interaction will be added into the model. If the two-sided Wald Chi-square p-value of the treatment by time interaction is less than 0.1 or if a visual examination of the K-M plot of the PFS indicates a delayed separation of the curves, the following analyses and potential other exploratory analyses will be conducted in order to report the treatment effect when taking into consideration of the delayed effect.
  - a) Delayed effect of immunotherapy interventions may cause a late separation in the PFS KM curves and non-proportional hazards. PFS (as determined by BICR) will be compared between treatment groups via a 2-sided max-combo test. The max-combo test statistic is the maximum of 4 different Fleming-Harrington family weighted log-rank test statistics.  $Z_m = \max(\text{FH}(0, 0), \text{FH}(0, 1), \text{FH}(1, 0), \text{F}(1, 1))$ , where  $\text{FH}(\rho, \gamma)$  are the test statistics from the Fleming-Harrington family of test statistics.  $\text{FH}(0, 0)$  corresponds to the log-rank test, while  $\text{FH}(0, 1)$  is more sensitive to late-difference alternatives,  $\text{FH}(1, 0)$  is more sensitive to early difference with decreasing treatment effect and  $\text{FH}(1, 1)$  uses weights at the median.
  - b) The estimates of the PFS hazard ratios will be estimated in 2 periods. The periods will be defined by a cut-off point. The optimal cut off point will be calculated using a stratified time-dependent Cox model with effects for treatment and period-by-treatment interaction. The optimal cut-off point will be estimated using a grid of possible cut-off points and obtained by maximizing the partial log likelihood. Ties will be handled using the exact method. A two-sided 95% CI for the hazard ratio's will also be presented.
- 2) The stratified log rank-rank test assumes same treatment effect among the different strata. The method of Gail and Simon will be used to test for a qualitative interaction between treatment and strata. This test will be conducted at  $\alpha=0.10$  level. The p-value reported from this specific analysis is for descriptive purposes alone.

Assess impact of Potential Prognostic Factors on Treatment Effect:

- 3) A multivariate Cox regression model will be used in order to estimate the treatment effect after adjustment for possible imbalances in known or potential prognostic factors. The factors used in the randomization, will be included in the model as stratification factors. However, all additional factors will be incorporated as covariates. The additional factors, which are all measured at baseline, will include:
- Age categorization ( $< 65$ ,  $\geq 65$ )
  - Gender (Male vs. Female)
  - Primary tumor location at initial diagnosis (GC, GEJ cancer, Esophageal Adenocarcinoma)
  - Disease status (locally recurrent/advanced, metastatic)
  - Lauren classification (intestinal type, diffuse type, mixed, unknown)
  - Peritoneal metastases (yes/no)
  - Prior surgery related to current cancer OR radiotherapy finished more than 6 months before randomization (yes/no)
  - Number of organs with baseline lesion (target or non-target;  $\leq 1$ ,  $\geq 2$ ) outside primary location (gastric, gastroesophageal junction and esophagus)
  - WHO histologic classification presence of signet ring cell (yes/no)

The level of the covariate normally associated with the worst prognosis will be coded as the reference level. The hazard ratio associated with treatment and with each of the baseline covariates will be presented along with associated 95% CIs.

- 4) The identification of the primary population using PD-L1 CPS  $\geq 5$  was introduced close to accrual completion. Therefore the randomization was not stratified by PD-L1 CPS  $\geq 5$ . The overall study population was stratified by
- PD-L1 expression level (tumor cells) ( $\geq 1\%$  vs.  $< 1\%$  or indeterminate)
  - Region: Asia vs. US vs. RoW
  - ECOG performance status: 0 vs. 1
  - Planned chemotherapy regimen (XELOX vs. FOLFOX)

As CPS $\geq 5$  is not a stratification factor, while pronounced imbalance is not expected due to the large sample size in this group, thorough review of data will be conducted and a sensitivity analysis may be conducted.

The distribution of baseline characteristics (demographics, disease characteristics and the stratification factors) between the two treatment arms will be inspected for potential imbalance in the subgroup of subjects with PD-L1 CPS  $\geq 5$ .

The distribution of these characteristics will also be assessed between the CPS PD-L1  $\geq 5$  subgroup and the overall population, regardless of treatment.

If a pronounced imbalance between the treatment arms is observed for one or several factors (eg,  $\geq 10\%$  difference between the frequency of the treatment arms for any level of the

categorical variables) a multivariate Cox regression model will be used in order to estimate the treatment effect after adjustment for those factors identified. The factors used in the randomization, will be included in the model as stratification factors and the factors identified with imbalance will be incorporated as covariates. For the purpose of fitting the multivariate model and easy interpretation of the results, any continuous variable identified will be dichotomized using a cut-off around median value and some sub-categories of a categorical covariate could collapsed due to small size of the sub-categories.

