#### **7.5.2.4 Analysis of Overall Survival**

OS in randomized CPS  $\geq 5$  subjects will be compared between nivo+chemo vs. chemo at the interim and final analyses, using stratified log-rank test, stratified by the stratification factors as specified in [Table 7.5-1](#). An O'Brien and Fleming  $\alpha$ -spending function will be employed to determine the nominal significance levels for the interim and final analyses (see [Table 7.5.1-1](#)). The stratified hazard ratio between the treatment groups will be presented along with 100\* (1 -  $\alpha$ )% CI (adjusted for interim) and will be calculated using a stratified Cox proportional hazards model, with treatment as the sole indicator covariate (for the nivo+chemo and chemo arm). Ties will be handled using the exact method.

OS will be estimated using the KM techniques. A two-sided 95% CI for median OS in each treatment group will be computed via the log-log transformation method. OS rates at fixed time points (eg, 12, 18, 24, 36 months, depending on the minimum follow-up) will be presented along with their associated 95% CIs. These estimates will be derived from the Kaplan Meier estimate and, corresponding CIs will be derived based on Greenwood formula for variance derivation and on log-log transformation applied on the survivor function.

The status of subjects who are censored in the OS KM analysis will be tabulated for each treatment group using the following categories:

- On-study (on-treatment, in follow-up)
- Off-study (lost to follow-up, withdraw consent, never treated)

A by-subject listing will be presented including treatment group, first and last dose date, whether the subject died, and if censored, the reason, event/censored date and OS duration.

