- 3) A multivariate Cox regression model will be used in order to estimate the treatment effect after adjustment for possible imbalances in known or potential prognostic factors. The factors used in the randomization will be included in the model as stratification factors. However, all additional factors will be incorporated as covariates. The additional factors, which are all measured at baseline, will include the same factors as in the PFS analysis.

The level of the covariate normally associated with the worst prognosis will be coded as the reference level. The hazard ratio associated with treatment and with each of the baseline covariates will be presented along with associated 95% CIs.

- 4) The identification of the primary population using PD-L1 CPS  $\geq 5$  was introduced close to accrual completion. Therefore the randomization was not stratified by PD-L1 CPS  $\geq 5$ . The overall study population was stratified by:
  - PD-L1 expression level (tumor cells) ( $\geq 1\%$  vs.  $< 1\%$  or indeterminate)
  - Region: Asia vs. US vs. RoW

- ECOG performance status: 0 vs. 1
- Planned chemotherapy regimen (XELOX vs. FOLFOX)

As  $CPS \geq 5$  is not a stratification factor, while pronounced imbalance is not expected due to the large sample size in this group, thorough review of data will be conducted and a sensitivity analysis may be conducted.

The distribution of baseline characteristics (demographics, disease characteristics and the stratification factors) between the two treatment arms will be inspected for potential imbalance in the subgroup of subjects with PD-L1  $CPS \geq 5$ .

The distribution of these characteristics will also be assessed between the PD-L1  $CPS \geq 5$  subgroup and the overall population, regardless of treatment.

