If a pronounced imbalance between the treatment arms is observed for one or several factors (eg,  $\geq 10\%$  difference between the frequency of the treatment arms for any level of the categorical variables) a multivariate Cox regression model will be used in order to estimate the treatment effect after adjustment for those factors identified. The factors used in the randomization, will be included in the model as stratification factors and the factors identified with imbalance will be incorporated as covariates. For the purpose of fitting the multivariate model and easy interpretation of the results, any continuous variable identified will be dichotomized using a cutoff around median value and some sub-categories of a categorical covariate could collapsed due to small size of the sub-categories.

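### The conditional baseline-imbalance model (item 4) splits imbalanced continuous covariates near the median and so under-corrects them; only a supportive estimate is affected

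*SAP*

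**What the plan says.** Item 4 of the supportive analyses notes that the CPS ≥ 5 population was adopted late and was not a stratification factor. The SAP's expectation is that "pronounced imbalance is not expected due to the large sample size in this group", but "thorough review of data will be conducted and a sensitivity analysis may be conducted". If one or more factors look clearly imbalanced, a Cox model stratified by the randomisation factors takes those factors as covariates. The example of a marked imbalance is a 10% or larger "difference between the frequency of the treatment arms for any level of the categorical variables". No criterion is given for continuous variables.

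For continuous factors the PFS text says "any continuous variable identified will be dichotomized using a cut-off around median value" and the OS text says "any continuous variable identified will be dichotomized using a cutoff around median value". Section 7.5.3.2 repeats the rule for nivolumab plus ipilimumab. The stated reasons are model fitting and ease of interpretation. Section 7.3.2 lists age, weight and the sum of target-lesion diameters among the baseline variables, so continuous candidates exist.

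Item 3 is a separate adjusted model with no imbalance condition attached. It uses a fixed factor list, including "Age categorization" at 65 years. For OS its factors "will include the same factors as in the PFS analysis". It contains no median split.

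The primary OS comparison is made "using stratified log-rank test, stratified by the stratification factors as specified in" Table 7.5-1, and its Cox model has treatment as the only covariate (section 7.5.2.4).

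**The concern.** Whether item 4 is run is conditional, but once it is run the split is mandatory. The model's stated aim is a treatment effect adjusted for the imbalance that was found. If one arm is older on average, it will also tend to be older within the younger half and within the older half, and a two-level indicator cannot see that. A factor would then be reported as adjusted for while part of its imbalance still sat in the treatment hazard ratio.

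The stated reasons carry little weight for a nuisance covariate. The treatment hazard ratio reads the same way whether age is entered as a line or as two groups, and a linear term is no harder to fit. The rule also fixes the cut-point only approximately, at a stage when the arms are already being compared. What is at stake is the credibility of this one sensitivity estimate.

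**Working it through.** **Inputs from the SAP.** Average OS hazard ratio 0.74; 800 final events among 949 subjects and power 97.9% (Appendix 5); 466 events and about 85% power at 35% prevalence (section 5.2.1); nominal final level 0.0252; 1:1 allocation; 489 CPS ≥ 5 subjects for nivolumab plus ipilimumab (Appendix 5, Table 3).

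**Inputs assumed, because the documents give none.** Covariate shape, prognostic strength per SD, and size of imbalance in SD.

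**Step 1: reproduce the plan's figures.** The SAP states no bias figure, so its power sets the scale. |ln 0.74| = 0.301. With Schoenfeld's formula:
- 800 events: Φ(√800/2 × 0.3011 − 2.238) = Φ(2.02) = 97.8%, against 97.9% stated.
- 466 events: Φ(√466/2 × 0.3011 − 2.238) = Φ(1.01) = 84.4%, against about 85% stated.

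The standard error of the log hazard ratio at 800 events is 2/√800 = 0.071.

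**Step 2: share of imbalance left by a median split.** For a covariate X with median m and density f, a small mean shift δ between arms changes the proportion above m by f(m)·δ. The two halves differ in mean by 2E|X − m|. The split therefore removes 2f(m)·E|X − m| of the shift, and leaves

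share = 1 − 2 f(m) E|X − m|.

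- Normal: 1 − 2 × 0.3989 × 0.7979 = 1 − 2/π = 36.3%.
- Uniform, unit SD: 1 − 2 × 0.2887 × 0.8660 = 50%.
- Right-skewed (lognormal), by simulation: about 22–27%.

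**Step 3: residual bias.** With β the log hazard ratio per SD, residual = β × δ × share. For a normal covariate and δ = 0.25 SD:

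| β per SD | Residual log HR | % of \|ln 0.74\| |
|---|---|---|
| 0.3 | 0.027 | 9 |
| 0.4 | 0.036 | 12 |
| 0.5 | 0.045 | 15 |
| 0.6 | 0.055 | 18 |

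With shares of 22% and 50% the two ends become 0.3 × 0.25 × 0.22/0.301 = 5.5% and 0.6 × 0.25 × 0.50/0.301 = 24.9%.

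**Step 4: chance imbalance at N = 949.** One standard error of a standardised mean difference is 2/√949 = 0.065 SD. For a normal covariate, as % of |ln 0.74|:

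| Imbalance | HR 1.2 per SD | HR 1.5 per SD | HR 2.0 per SD |
|---|---|---|---|
| 1 SE (0.065 SD) | 1.4 | 3.2 | 5.4 |
| 2 SE (0.13 SD) | 2.9 | 6.4 | 10.9 |

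**Step 5: how unusual 0.25 SD is.** At N = 949 it is 0.25/0.065 = 3.9 SE (p about 0.0001 per covariate). At N = 489 it is 0.25/0.090 = 2.8 SE (p about 0.006).

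**Step 6: check by simulation.** Large-sample Cox fits used the SAP's OS hazards, a hazard ratio of 1 then 0.65, 25.4 months of accrual (uniform entry assumed) and analysis at 49.4 months. Opposite directions of imbalance were averaged. For a normal covariate at 0.25 SD, the split left 5.4%, 11.6% and 17.3% of |ln 0.74| at HR 1.2, 1.5 and 2.0 per SD. The closed form gives 5.5%, 12.3% and 21.0%. A correctly specified linear term left about zero.

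**The case against.** The strongest reply is that item 4 is one optional supportive analysis and the SAP does not expect it to be needed. That stands. Three stronger readings are tempting, and the documents do not support them.

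- **A reader might infer that the SAP's adjusted Cox models all split every continuous covariate at the median.** Only item 4 does. Item 3 uses fixed categories, such as age at 65.
- **A reader might infer that item 4 is the plan's only protection for an unstratified primary subgroup.** It is not. Treatment was randomised, and CPS scoring was blinded to arm (section 2.3). The primary analyses are stratified by four factors, and item 3 adjusts for further prognostic factors without waiting for an imbalance.
- **A reader might infer that 0.25 SD is the SAP's own trigger, and so that a bias of 10–20% follows from the plan.** A 0.25 SD shift in a normal covariate does move the proportion above the median by 0.25 × 0.3989 = 10 points. But the SAP's 10% is an example for levels of categorical variables, and carrying it over to a continuous scale is the reader's own step. The prognostic strength needed is also an assumption.

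A further caution concerns simulation. The gap between split and continuous fits in one direction of imbalance overstates the residual, because Cox hazard ratios are non-collapsible. With no imbalance at all, that gap was already about 2–5% of |ln 0.74| at β of 0.3–0.6. The closed form and the two-direction average avoid this.

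None of this supplies a statistical reason for the split.

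**Conclusion.** The point holds as a minor one, confined to item 4 of the three sections. When that model is triggered by a continuous covariate, the median split leaves about 36% of the imbalance in place if the covariate is normal with a linear log-hazard effect, and roughly 22–50% across the shapes tried. The resulting bias is about 9–18% of |ln 0.74| at an assumed 0.25 SD imbalance and log hazard ratio of 0.3–0.6 per SD. It is about 1–6% at 1–2 standard errors of imbalance and hazard ratios of 1.2–1.5 per SD.

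Even at 0.25 SD and a hazard ratio of 1.5 per SD, the residual is 0.405 × 0.25 × 0.363 = 0.037. That moves 0.74 to about 0.71 or 0.77, roughly half a standard error. The split still removes about 60–65% of the unadjusted shift for a normal covariate. The primary log-rank tests, alpha allocation and power are untouched.

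**What to change.** In item 4 of sections 7.5.2.2, 7.5.2.5 and 7.5.3.2, replace the median split with continuous entry: linear, log-transformed if skewed, or a restricted cubic spline. Preferably enter age continuously in item 3 as well. Keep categories for descriptive tables and forest plots. It would also help to say what counts as imbalance for a continuous variable, for example a standardised difference, since the current example covers only categorical ones.

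The cost is a sentence of SAP text and one model term. A linear term uses the same single degree of freedom as the split, and a 3-knot spline uses one more. No new data are needed. SAP version 5.0 was written after the nivolumab plus chemotherapy PFS and interim OS analyses (Document History), so for those the change would be a supplementary re-run. It is most useful for the final OS and the nivolumab plus ipilimumab analyses.
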